## 8.6 Subject Withdrawal/Study Completion

Subjects will complete the study after the 3 month follow up visit. For a subject who withdraws from the study, all data collected up to the point of withdrawal is retained. A subject wishing to withdraw from the study should provide that request in writing to the site to document the decision.

## 8.7 Protocol Deviations

A protocol deviation is defined as an event where the clinical investigator or site personnel did not conduct the study per the protocol or the Investigator/Trial Agreement.

No protocol deviations will be made to the investigational plan. The investigator is required to adhere to local EC procedures for reporting deviations.

# 9 ADVERSE EVENTS

## 9.1 AE Definitions

### Adverse Event (AE):

Any untoward medical occurrence, unintended disease or injury, or untoward clinical signs in subjects, whether or not related to the use of the study device or procedures.

### Serious Adverse Event (SAE):

Any untoward medical occurrence that meets any of the following criteria:

- Resulted in death
- Resulted in inpatient hospitalization or prolonged an existing hospitalization
- Resulted in a life-threatening illness or injury (patient in immediate danger of death)
- Resulted in permanent impairment of a body function or permanent damage to a body structure
- Necessitated medical or surgical intervention to prevent life-threatening illness or injury or permanent impairment of a body function or body structure

A life-threatening adverse event means any adverse event that places the patient, in the opinion of the Principal Investigator, at immediate risk of death from the reaction as it occurred, i.e., it does not include a reaction that, had it occurred in a more severe form, might have caused death.

A planned hospitalization for a pre-existing condition, without a serious deterioration in health, is not considered a serious adverse event.

### Adverse Device Effect (ADE):

An ADE is an adverse event related to the use of a medical device. An event should be considered related to the device when it is the result of: insufficient or inadequate instructions for use or any malfunction of the device.

An event should be considered not related to the device when it is the result of: a pre-existing medical condition, a new illness, injury or condition, or due to medication.

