### 3 BACKGROUND

#### 3.1 Overview

Stroke is the second single most common cause of death in Europe accounting for almost 1.1 million deaths each year, based on data from WHO estimated the number of strokes in the year 2000. Furthermore, it has been predicted that stroke incidence will increase to 1.5 million per year by 2025, largely owing to the increasing proportion of elderly individuals.

Ischemic strokes represent approximately 87% of all strokes while the remaining 13% are hemorrhagic. The chief goal in treating acute ischemic stroke is to restore cerebral blood flow as rapidly and safely as possible. Currently there are two approaches to treatment, intravenous (IV) delivery of Tissue Plasminogen Activator (tPA), a thrombolytic agent, and mechanical thrombectomy. Combining IV tPA treatment with mechanical thrombectomy has recently been shown to demonstrate an advantage with good clinical results for patients.

Endovascular treatment using mechanical devices to recanalize the occluded vessel include the use of catheters to directly deliver a clot-disrupting or retrieval device to the thrombus, this includes aspiration catheters, stent-retrievers and other clot disrupting devices. However, withdrawing the clot disrupting devices by mechanical force to perform thrombectomy may increase the risk of vascular intimal injury and the incidence of vasospasm. Therefore, aspirating clot may be preferred to reduce vessel damage during recanalization. Mechanical revascularization using an aspiration catheter as the primary approach to clot removal is commonly performed and

[figure not shown]
sometimes referred to as the ADAPT technique. The ADAPT technique is favored by some physicians because of its potential to be less traumatic to the neurovasculature and improve on time to revascularization compared to stent retrievers.

The MIVI Neuroscience, Inc. CE Marked Q Aspiration Catheter is a family of short, extension catheters introduced through an 8F guide catheter/6F sheath. Aspiration is performed from the short Q Catheter into the guide catheter/sheath. The MIVI Neuroscience, Inc. Q Aspiration Catheter may offer an increased force of aspiration from the larger 8F guide lumen and the potential access to more distal clot with the small Q Catheter lumen.

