### **Unanticipated Adverse Device Effect (UADE):**

An unanticipated adverse device effect is defined as “any serious adverse device effect which by nature, incidence, severity or outcome has not been identified in the current risk analysis. Those known adverse events related to the device are listed in the IFU.

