## **9.2 Adverse Event Reporting**

In the case of any serious adverse effects (SAE) or complications reported by patients or by the attending clinician attributable to the use of the device, the event will be reported to the EC and CA, as applicable, per standard post-market device monitoring.

All serious adverse events, and/or device deficiencies that may have led to an ADE and is serious must be reported to the Sponsor within a reasonable time of the Principal Investigator becoming aware of the event and without an unjustified delay.

The Sponsor can be contacted at the following:

Email Address	[contact]
[contact]
[contact]

The Investigator shall assess adverse events according the definitions set out in this protocol and determine seriousness and relationship to the device.

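### The rule for calling an event device-related is narrower than the ADE definition it serves, so vessel injury from a normally working catheter may be labelled not device-related or labelled differently across sites

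*Combined protocol and SAP*

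**What the plan says.** Section 9.1 opens its entry on adverse device effects in general terms: "An ADE is an adverse event related to the use of a medical device". The next sentence says when an event should be considered related, and gives two causes: "insufficient or inadequate instructions for use or any malfunction of the device". A matching sentence says an event is not related when it results from "a pre-existing medical condition, a new illness, injury or condition, or due to medication".

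Section 9.2 makes these definitions the standard for assessment: "The Investigator shall assess adverse events according the definitions set out in this protocol and determine seriousness and relationship to the device". The UADE entry in Section 9.1 builds on the ADE label, since a UADE is "any serious adverse device effect which by nature, incidence, severity or outcome has not been identified in the current risk analysis".

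Other sections use wider language. The trigger in Section 9.2 for reporting to the ethics committee (EC) and competent authority (CA) covers serious events or complications "attributable to the use of the device, the event will be reported to the EC and CA, as applicable". It mentions neither malfunction nor instructions. Section 8.3 collects procedure-related as well as device-related adverse events, but Section 9.1 does not define the former.

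**The concern.** Use in accordance with the IFU is an inclusion criterion (Section 6.3). An injury caused by an intact, correctly used catheter is therefore a central case for this study, and it is the case the two-cause rule leaves out. Use error is not named as a cause either.

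The matter bears on the study's purpose, which is to demonstrate safety and performance (Section 4.1). Section 3.1 says that pulling back clot-disrupting devices "may increase the risk of vascular intimal injury and the incidence of vasospasm", and gives this as a reason why aspiration may be preferred. Section 5.3 says there are no clinical investigation data yet. Vessel injury attributable to the catheter is thus among the things a reader of the final report will want to know.

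The protocol describes no central review of causality that would correct a site's label. A clinical events committee appears only in the abbreviation list, and the core laboratory's stated tasks are mTICI and embolization.

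**Working it through.** The documents state no ADE rate or relatedness figure, so there is nothing to reproduce. The check is a comparison of provisions. The test case is a vessel injury caused by a catheter that works as intended, is used as instructed, and comes with adequate instructions.

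| Provision | Does the test case meet it? |
|---|---|
| 9.1, first sentence of the ADE entry (related to use) | Yes |
| 9.1, cause 1: inadequate instructions | No, by construction |
| 9.1, cause 2: malfunction, which 13.3 defines as an unexpected change to the device | No, the device is unchanged |
| 9.1, not-related list, which includes a new injury | Arguably yes |
| 8.3, procedural data: procedure- or device-related events | Yes if called procedure-related, a term left undefined |
| 9.2, EC/CA trigger: attributable to use | Yes |

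The same injury is thus related under one sentence of Section 9.1, meets neither cause listed in the next, and can be placed under the not-related list. Two sites could label it oppositely, each relying on the same entry.

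What follows if the label is not related:

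- **Serious event.** It is still an SAE. SAEs are collected from the procedure to the 3-month visit (Table 3), and all of them go to the sponsor (Section 9.2). Section 7.1 separately requires investigators to notify the EC of SAEs under local procedures. The event cannot be a UADE, because a UADE must first be a serious device effect.
- **Non-serious event.** Sections 8.4 and 8.5 and Table 3 list serious events only. The one listed collection point for non-serious events is Section 8.3, which is limited to procedure- and device-related ones. If the event is called neither, it may not be recorded.
- **Endpoints.** sICH, embolization to a new territory and all-cause mortality (Section 13.2) carry no relatedness condition and do not change.

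For scale only, take N = 50 (Section 6.2) and an assumed rate p of such injuries. The expected number is 50p, and the chance of at least one is 1 − (1 − p)^50.

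| Assumed p | Expected events | Chance of at least one |
|---|---|---|
| 1% | 0.5 | 39.5% |
| 2% | 1.0 | 63.6% |
| 5% | 2.5 | 92.3% |
| 10% | 5.0 | 99.5% |

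If 3 of 50 subjects had such an injury and every one were labelled not related, 3/50 = 6.0% (exact 95% interval 1.25% to 16.55%) would be shown as 0/50 = 0% (upper limit 1 − 0.025^(1/50) = 7.1%). With 2 of 50, 4.0% (0.5% to 13.7%) would be shown as 0%. The plan does not call for confidence intervals; they are given here only to show the precision at this sample size.

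**The case against.** The strongest reply is that the two causes need not be exhaustive. The text says an event is related when one of them applies; it does not say only when. The sentence before is broad, Sections 8.3 and 9.2 are broad, and the UADE entry adds that known device-related events are listed in the IFU. A sensible investigator could call a perforation by an intact catheter device-related on the strength of those passages. This stands: the document is inconsistent with itself rather than plainly exclusive, so mislabelling is possible, not certain.

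A reader might go further and infer that such injuries are not counted at all, or that serious ones would escape regulatory reporting. The documents do not support either. Serious injuries are reported as SAEs whatever their relatedness, and the EC/CA trigger has its own, wider wording. Embolization to a new territory is not lost either, because it is an endpoint judged by the core laboratory.

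Two further limits stand. The effect on UADE status matters only for events not already identified in the risk analysis, which is not among the documents. And no ADE rate is a named endpoint, no hypothesis is tested, and the illustrative counts come from no document.

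The reply does not remove the conflict inside Section 9.1. The two-cause sentence is the only one that says what makes an event related, the not-related list offers a place for a new injury, and Section 9.2 directs investigators to these definitions. Section 9.3 mentions user error, but only for a device that deforms or breaks. Section 8.3 mentions procedure-related events, but nothing in Section 9.1 tells a site how to separate them from device-related ones.

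**Conclusion.** The point holds as an inconsistency in the safety classification. The working rule is narrower than its own opening sentence and than Sections 8.3 and 9.2, so a vessel injury from a normally functioning catheter may be labelled not device-related, or labelled inconsistently. Three things are exposed: the device-related count, which may be understated; UADE status, for serious events not already in the risk analysis; and capture of non-serious injuries that are not called procedure-related.

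The conclusion that device-related harm is understated would be too strong. It would require the two-cause list to be exclusive and such injuries to occur, and the documents establish neither. The size is unknown; 6.0% shown as 0% rests wholly on an assumed 3 events in 50 with all three labelled not related.

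**What to change.** Reword Section 9.1 so that an event is device-related when it results from use of the device, including a device that functions normally, from use error, from inadequate instructions, or from malfunction. State that the new-injury item in the not-related list excludes injuries caused by the device or the procedure. Define procedure-related events separately, since Section 8.3 already collects them, and tabulate device-related and procedure-related events side by side in the safety summary.

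The cost is definition wording and one CRF field, submitted to the ethics committees as an amendment under Section 7.1. The device-related count may come out higher.

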### **Unanticipated Adverse Device Effect (UADE):**

An unanticipated adverse device effect is defined as “any serious adverse device effect which by nature, incidence, severity or outcome has not been identified in the current risk analysis. Those known adverse events related to the device are listed in the IFU.

## **9.2 Adverse Event Reporting**

In the case of any serious adverse effects (SAE) or complications reported by patients or by the attending clinician attributable to the use of the device, the event will be reported to the EC and CA, as applicable, per standard post-market device monitoring.

All serious adverse events, and/or device deficiencies that may have led to an ADE and is serious must be reported to the Sponsor within a reasonable time of the Principal Investigator becoming aware of the event and without an unjustified delay.

The Sponsor can be contacted at the following:

Email Address	[contact]
[contact]
[contact]

The Investigator shall assess adverse events according the definitions set out in this protocol and determine seriousness and relationship to the device.

## **9.3 Device Malfunction/Failure**

Device malfunctions or failures will be reported per post market device reporting requirements. The following situations should be reported:

- All situations where the device is physically defective, including out of the box failure;
- All situations where the device physically deforms or breaks, even if caused by user error;
- All situations where the device mechanically fails to perform as intended.

# **10 STATISTICAL DESIGN AND ANALYSIS PLAN**

## **10.1 Study Design Justification**

This is a multi-center study involving up to 50 subjects at up to 5 investigational sites in Spain. The purpose of the study is to collect data on the safety and performance of the Q Aspiration Catheter used to remove thrombi and emboli from the neurovasculature during acute ischemic stroke. The primary safety endpoint for this study symptomatic intracranial haemorrhage within 24 hours post-procedure along with an NIHSS change of >4. The primary performance endpoint is successful revascularization of the target artery defined as mTICI 2b-3 flow at the end of the procedure.

## **10.2 Statistical Methods**

This study is a single arm, registry study with endpoints compared to well defined and published outcomes. This study is designed for observational data to be collected and reported. There will be no formal statistical hypothesis testing conducted, and therefore sample size is not based on power calculations.

Data analysis will comprise of descriptive statistics (means, standard deviations, rates, correlations, etc.) on the variables detailed in the study endpoints and other data collected.

The analyzed population will consist of all subjects who signed an informed consent form.

### **10.3 General Statistical Considerations**

All endpoints will be analyzed descriptively. In general, continuous parameters will be summarized by number of evaluable observations, mean, standard deviation, median, minimum, and maximum. Categorical data will be described by frequency counts and percentages.

Every effort will be made to collect complete data. Unless otherwise specified, imputation of missing data will not be performed. Given the timing for evaluation, missing data is expected to be minimal to none for the primary safety and effectiveness endpoints. The primary analysis for the primary endpoints will include all subjects in the analysis population.

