### **6.2 Number of Subjects**

Up to 50 subjects may be enrolled at up to 5 investigational sites in Spain. A center may enroll a maximum of twenty subjects.

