## **7.2 Subject Information and Consent**

Subjects must be informed about the study prior to enrollment. Only those subject's (or subject's legal representative) who voluntarily provide written consent will be allowed to participate in the study. The original signed consent form should be retained in the patient's study records and a copy should be provided to the patient or legal representative. If the patient is unable to provide informed consent or is deceased prior to consenting, a legally authorized representative may consent to use the patient's medical record.

A sample informed consent document suitable for use in this study will be provided. Iterations of this document must be approved by the reviewing Ethics Committee and the sponsor or sponsor-designate. Subjects must be presented with the most current EC approved version of the consent form for signature and study enrollment. The consent form and consent discussion should be in a language the subject understands. No study related data may be collected prior to patient consent. Study subject's must be consented prior to or at the study 3 month visit.

Subjects may withdraw participation at any time during the investigation without sacrificing their rights as a patient or compromising their quality of medical care.

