# **8 STUDY PROCEDURES**

## **8.1 Screening and Enrollment**

All patients diagnosed with acute ischemic stroke who undergo mechanical thrombectomy with the Q Aspiration Catheter as first line therapy, without regard to gender, are eligible for screening to participate in the clinical study. Patients will be screened based on the study inclusion and exclusion criteria after the procedure.

A screening log should be kept of all subjects in whom the Q Aspiration Catheter was used to prevent bias in subject selection. Death may be added to the screening log as reason for screen failure, if applicable.

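### Binary endpoints from at most 50 subjects are to be compared with published outcomes, but the plan summarises them by counts and percentages only, with no confidence interval

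*Combined protocol and SAP*

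**What the plan says.** Section 10.2 describes the design in these words: "This study is a single arm, registry study with endpoints compared to well defined and published outcomes". It then disclaims inference: "There will be no formal statistical hypothesis testing conducted, and therefore sample size is not based on power calculations". The methods sentence in the same section is open-ended: "Data analysis will comprise of descriptive statistics (means, standard deviations, rates, correlations, etc", and the list closes there.

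Section 10.3 gives the summaries. Continuous variables get the number of evaluable observations, mean, standard deviation, median, minimum and maximum. For the rest, "Categorical data will be described by frequency counts and percentages". Missing data are not imputed unless otherwise specified.

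On size, section 6.2 states: "Up to 50 subjects may be enrolled at up to 5 investigational sites in Spain". This is a ceiling; the section sets no minimum.

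All six endpoints in sections 4.2 and 4.3 are yes/no outcomes: final mTICI 2b-3, symptomatic intracranial haemorrhage (sICH), mTICI 2b-3 with the Q Catheter alone, embolization to a new territory, mRS 0-2 at 90 days, and death by 90 days. No expected or reference rate is given for any of them. The seven references in section 15 are cited only in the background, section 3.1.

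**The concern.** A comparison of a single-arm rate with a published rate needs two things: the rate to compare with, and some idea of how far the observed rate could lie from the true one by chance. The plan promises the comparison. For the binary endpoints, which are all of the endpoints, it specifies only the point estimate. The standard deviation in section 10.3 belongs to continuous variables and does not serve here.

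What is at stake is how the result is read. An sICH result of 0% beside a published rate of a few percent would look like an advantage, and 80% revascularization beside a somewhat higher or lower figure would look like a difference. With at most 50 subjects, neither reading need be justified. Because section 4.1 speaks of demonstrating safety and performance, a reader is likely to draw a conclusion from the comparison.

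**Working it through.** **Is there a figure to reproduce?** No. The cap of 50 has no stated alpha, power, rate, margin or precision target behind it, and section 10.2 says that it is not power-based. The check is therefore how much sampling error the planned summary leaves unseen.

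**Inputs**
- n = 50: the maximum in sections 4.1, 6.2 and 10.1.
- Two-sided 95% level: assumed, since the plan states none.
- Observed counts k: assumed, since the plan gives no expected rates. They illustrate rare safety events, a rate near one half, and a high success rate.

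**Formula.** Exact (Clopper-Pearson) limits for k events in n subjects: lower = Beta(0.025; k, n−k+1) and upper = Beta(0.975; k+1, n−k), both as quantiles. For k = 0 the lower limit is 0 and the upper is 1 − 0.025^(1/n).

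**Results at n = 50**, with Wilson limits as a check on the choice of method:

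| Illustration | k/n | Observed | Exact 95% | Wilson 95% |
|---|---|---|---|---|
| sICH, no events | 0/50 | 0% | 0–7.1% | 0–7.1% |
| sICH, two events | 2/50 | 4% | 0.5–13.7% | 1.1–13.5% |
| mRS 0-2 | 25/50 | 50% | 35.5–64.5% | 36.6–63.4% |
| mTICI 2b-3 | 40/50 | 80% | 66.3–90.0% | 67.0–88.8% |

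Zero events worked through: 1 − 0.025^(1/50) = 7.1%. If only 40 subjects were enrolled, 1 − 0.025^(1/40) = 8.8%.

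The exact intervals span 64.5 − 35.5 = 29.0 points at 25/50 and 90.0 − 66.3 = 23.7 points at 40/50. Over all counts at n = 50, the exact and Wilson limits differ by at most 1.2 points, so the method does not drive the conclusion.

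**The zero-event case from the other side.** If the true sICH rate were 4%, the chance of seeing none in 50 subjects would be (1 − 0.04)^50 = 13.0%. At a true rate of 2% it would be (1 − 0.02)^50 = 36.4%. An observed 0% is thus compatible with rates that are not zero.

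**Endpoint definition.** A published rate can be matched only to a fixed definition, and the sICH wording differs between sections:
- Section 4.2: at 24 hours, with an NIHSS change of at least 4.
- Section 10.1: within 24 hours, with an NIHSS change above 4.
- Section 13.2: the ECASS II definition, with an increase of 4 points or more or bleeding that leads to death, from data within 24 hours but with a 0–36 hour window in brackets.

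These cannot all be the definition that is compared with one published figure.

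**The case against.** The strongest reply is that the plan is openly observational. It tests nothing, sets no success rule, and section 10.1 words the purpose more modestly than section 4.1, as collecting data. Counts and percentages suit such a study. The open list in section 10.2 leaves room for an interval, and a reader can compute one from a count and its denominator. The widths above come from the small sample, not from the omission.

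Most of this stands, and it limits the point to one of reporting. It does not remove the point: a confidence interval is itself descriptive, and a study that says it will compare rates should show how precise they are instead of leaving each reader to work it out.

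Some stronger readings are tempting but not supported:
- *The study needs a hypothesis test, a power calculation or more subjects.* Section 10.2 declares their absence as a design choice, and nothing in the plan depends on a formal decision.
- *The comparator will be picked to suit the data.* The text permits a late choice but does not plan one. The unnamed source is mainly missing detail.
- *Denominators will be hidden.* For the primary endpoints this is weak: section 10.2 defines the analysed population as all consented subjects, and section 10.3 includes all of them in the primary analysis and expects little or no missing data. The matter has more force for the 3-month mRS, because the evaluable number is listed for continuous variables but not for categorical ones.
- *The interval would repair the comparison.* It would not. Clustering by centre and selection through consent after the procedure are separate matters, which an interval does not address and which form no part of this point.

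**Conclusion.** The point holds as a cheap improvement. The plan commits to comparing six binary endpoints with published outcomes and specifies for them a summary that shows no sampling error. At the maximum of 50 subjects that unseen error is material: an upper limit of 7.1% after no events, and an interval about 24 to 29 points wide for observed rates of 80% and 50%. Fewer subjects would make it larger.

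The counts and the 95% level are assumptions, and the figures illustrate precision; they do not predict results. That all six endpoints are binary, that section 10.3 gives only counts and percentages for them, and that no interval is pre-specified can be read directly from the document. A reader might infer that the descriptive design is invalid or the sample too small for its purpose; the documents do not support that.

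**What to change.** In section 10.3, add that each binary endpoint is reported as count, denominator and two-sided 95% exact (Clopper-Pearson) confidence interval. Where a published rate is shown, the interval is set beside it descriptively, with no test, no success rule and no change in sample size. Add one sentence saying that the interval reflects this study's sampling error only.

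As a supporting step in section 10.2, fix before data review the published source, its value and its endpoint definition for each comparison. The sICH wording in sections 4.2, 10.1 and 13.2 must be reconciled first, so that the published rate can be matched to one definition.

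The cost is a few lines of text and code, with no extra subjects, visits or data. The downsides are slightly more reporting, an earlier choice of published sources and a more modest claim. The interval could also be over-read as covering all uncertainty, which is why its limit should be stated next to it.
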